### **6.1.3.1 Graphical presentation of results**

Model estimated means with 90% credibility intervals will be used to present the results over time.

### **6.1.4 Supportive analyses**

Corporate Confidential Information

### **6.1.5 Sensitivity analyses**

A sensitivity analysis will be performed on the primary endpoint adding PET positivity (yes/not) prior to randomization a factor. The same analysis as defined in Section 6.1.3 will be performed, and adding PET positivity as a covariate in the model.

A further sensitivity analysis may be performed using an LOCF imputation for missing values. The main purpose of this analysis will be the investigation of potential bias, caused by subjects excluded from the analysis due to prohibited concomitant medication use (as concomitant medication increase is primarily due to poor response). However, the analysis will not be restricted to these subjects. A summary of prohibited medication incidence (as defined by the Protocol Deviations database), will be produced which will present the number of subjects with COMD01 deviations and time to first COMD01 deviation by treatment group, this summary will serve to decide whether the LOCF analysis will be performed.

## **6.2 Secondary objectives**

### **6.2.1 Variables**

Secondary variables for this study are:

- [F-18]FDG-PET/CT
- HRCT
- Pulmonary function tests: Change from baseline in absolute and % predicted FVC, FEV1, FEF25-75, FEV1/FVC, FEV3, FEV3/FVC, FEV6, TLC, RV, RV/TLC, DLCO, and post-bronchodilator FEV1/reversibility and other parameters as needed
- 6MWT outcomes: Change from baseline in distance, oxygen saturation, hearth rate and Borg Questionnaire score

For the pulmonary function test parameters the direction of benefit is as follows

- an increase in values is beneficial: absolute and % predicted FVC, FEV1, FEF25-75, FEV1/FVC, FEV3, FEV6, FEV3/FVC, DLCO
- a decrease in values is beneficial: RV, TCL, RV/TCL.

### [F-18]FDG-PET/CT

The [F-18]FDG-PET/CT imaging data will be analyzed to identify the max standardized uptake values in the following categories:

- A maximum of 5 focal nodal uptake regions (mediastinal, hilar)
- A maximum of 5 focal regions of uptake in lung parenchyma
- A maximum of 5 extra-thoracic focal uptake regions on the whole body scan [F-18]FDG-PET/CT mean
- Reference regions
  - Lung parenchyma, unaffected by focal lesion uptake
  - Ascending aorta blood pool

The mean of the SUVmax values (resp. SUVmean) for each category will be taken to obtain one SUVmax value (resp. SUVmean) per patient / time point / category. The percent change from initial scan mean SUVmax values (resp. SUVmean) will be used for all analysis.

Also the change in the individual lung nodules will be examined, using a discretized scale of complete response (CR), partial response (PR), stable disease (SD) and progressive disease (PD) as in the oncology European Organization for Research and Treatment of Cancer criteria for [F-18]FDG-PET/CT (Young et al, 1999).

### High resolution computed tomography

The HRCT scans will be evaluated using the following HRCT scoring systems:

- Parameters provided by Paraxel\*:
  - total parameter score
  - total sarcoidosis score
  - and HRCT results evaluated for worsening, improvement, or stable outcome by independent reviewer(s)
- Parameters provided by MedQIA read-out:
  - Key: Percentage air trapping in the whole lung
  - Secondary: Percentage air trapping at the lobar level (i.e. by location)

and HRCT results evaluated for worsening, improvement, or stable outcome by two independent assessors consolidated into one reading by MedQIA. Change in HRCT total score from initial scan will be used for analysis.

Details on the derivations of these scores are provided in the study's independent imaging charter and they will be included in the source database.

\*Where multiple reviewers have assessed the Paraxel HRCT, the worse results will be selected for categorical summaries and the mean will be used for the continuous.

### **6.2.2 Descriptive analyses**

All secondary variables will be listed by treatment, subject and visit/time. Descriptive statistics will be provided by treatment and visit/time for all continuous variables. Summary statistics will include arithmetic mean, SD, CV (arithmetic), median, minimum and maximum. Graphical methods will be employed to show mean (SD) figures for raw or derived value (such as change from baseline or percent change from baseline) for each endpoint.

Incidences of patients with complete response (CR), partial response (PR), stable disease (SD) and progressive disease (PD) will be summarized by treatment group over time, patients who discontinue for lack of efficacy will be treated as a separate category in this summary. The best response by subject will also be summarized by treatment group; CR is the best possible response and will supersede any previous response of PR or SD. PR will supersede SD. If a subject has a response of PD this is the only best response they can have.

The correlation between changes from initial FDG-PET scan in SUVmax and changes from baseline in FVC, FEV1, PROs, 6MWT distance will be assessed with scatterplot grids. As we may not be able to assume normality of the data, Kendall's tau-b coefficients and its corresponding p-values will be displayed to assess correlation.

Summary stats by PET positivity will be provided for the analyses on:

- PET data
- HRCT total scores
- 6MWT
- FEV1,FEV3,FEV6 (L as well as % of predicted)

Data on new lesions from [F-18]FDG-PET/CT will be only listed.

### **6.2.3 Statistical model, assumptions and hypotheses**

#### **[F-18]FDG-PET/CT**

The mean percent change from baseline in SUVmax in the nodules at week 12 will be analyzed using ANCOVA with baseline SUVmax as a covariate and treatment as factor.

The same analysis as for the percent change from baseline in mean SUVmax in the nodules will be performed for the percent change from baseline in SUVmax in the lung parenchyma and the extra-thoracic regions, where available, at week 12. It will also be repeated for SUVmean in the parenchyma.

The percentage of patients with at least 50% reduction of SUVmax in nodules will be analyzed via logistic regression with baseline SUVmax as a covariate and treatment and PET positivity (yes/no) prior to randomization as factors.

The same sensitivity and subgroup analyses as the primary may also be performed, if deemed necessary.

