### 3        Investigational plan

#### 3.1      Study design

Figure 3-1      Study Design scheme

This is a 32-week, subject- and investigator-blinded, randomized, placebo-controlled, parallel-group, non-confirmatory study to assess the clinical efficacy of ACZ885 administered subcutaneously (s.c.) in 6 injections given 28 days apart (Figure 3-1). The study will randomize approximately 38 patients (targeting 30 completers) with evidence of parenchymal involvement and histologically proven, chronic pulmonary sarcoidosis of  $\geq 1$  year duration with persisting activity at baseline despite background therapy as determined by clinical history, radiologic evidence (e.g. HRCT, MRI or chest x-ray), spirometry and MMRC dyspnea scale assessments. Randomization will be stratified by positive PET parenchymal tracer uptake (yes/no). Acceptable background therapy includes a stable regimen of prednisone  $\leq 15$  mg/day and/or no more than one immune suppressive agent (i.e., methotrexate, azathioprine, leflunomide or hydroxychloroquine).

Re-screening of subjects may be allowed with the consultation of the Sponsor's medical expert.

For each subject, there will be a maximum 40-day screening period. Screening is valid for 40 days from the time of the first screening assessment. [F-18]FDG-PET/CT scans obtained locally at the study site within 8 weeks of randomization will be acceptable for baseline assessment prior to receiving the first injection of ACZ885. However, any prior [F-18]FDG-PET/CT imaging must also have been done without changes in treatment during the subsequent period leading up to study randomization.

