Subjects who meet the eligibility criteria at screening will undergo evaluation of full baseline clinical and biomarker assessments prior to injection. Baseline assessments including safety laboratory evaluations and pulmonary function tests will not be available prior to dosing and for those measures eligibility criteria will be determined based on the screening results. Enrolled subjects will be randomized at a 1:1 ratio to receive treatment with either ACZ885 or placebo. On Days 1, 29, 57, 85, 113 and 141 patients will be administered s.c. dosing with ACZ885 at 300 mg or corresponding placebo treatment. All patients will return to the study center for safety and pharmacokinetic (PK) checks on an every four week basis at which time they will receive either study treatments depending on treatment arm. Additionally, patients will undergo clinical assessments that include pulmonary function tests with lung volumes, DLco, 6MWT, and clinical outcome assessments as outlined in the [Assessment Schedule](#).

At week 12, a second [F-18]FDG-PET/CT will be obtained. In addition, functional clinical measures Corporate Confidential Information will take place at this time point. The final dosing will take place on week 20, followed by a visit on week 24 Corporate Confidential Information

Corporate Confidential Information. Also included at the week 24 visit is the second HRCT assessment. Patients return for the end of study (EOS) visit at week 32.

A follow-up visit or phone call for SAEs must be performed 30 days following early discontinuation, or 8 weeks after last injection of study drug, whichever is later. If anaphylactic reactions occur after injection, two more immunogenicity samples (at the time of the event and 8 weeks later) need to be taken. Any patient who discontinues the study early will complete the Week 32, EOS visit. Patients discontinuing after week 12 will also undergo a second HRCT assessment at this visit, as assessed on a case-by-case basis by the Sponsor.

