## **4 Population**

This study will recruit patients with chronic active pulmonary sarcoidosis as defined by disease duration  $\geq 1$  year with evidence of persistent or progressive parenchymal changes as characterized by radiological evidence. A total of approximately 38 patients will be randomized to participate in the study. The sample size will be re-estimated at the interim analysis and number of randomized patients may be increased up to a maximum of 90.

The investigator must ensure that all subjects being considered for the study meet the following eligibility criteria.

Subject selection is to be established by checking through all inclusion/exclusion criteria at screening and first baseline prior to the first injection. Safety laboratory evaluations and pulmonary function tests taken at first baseline will not be available prior to first injection, and screening values should be used for inclusion in the study. A relevant record (e.g., checklist) of the eligibility criteria must be stored with the source documentation at the study site.

Deviation from any entry criterion excludes a subject from enrollment into the study.

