### 8.5.2.1 [F-18] FDG-PET/CT

In this study, [F-18]FDG-PET/CT imaging will provide early evidence for anti-inflammatory effects of IL-1 $\beta$  blockade by ACZ885 on the sarcoidosis process. [F-18]FDG-PET/CT has been shown to detect lung parenchymal involvement at any chest x-ray (CXR) stage, including therapy-resistant disease, and can also provide information on extra-pulmonary disease. Lung fluorodeoxyglucose (FDG) uptake in sarcoidosis has been shown by PET imaging to correlate with important sarcoidosis BAL biomarkers, including percentage neutrophils and CD4:CD8 ratio. In two previous sarcoidosis trials, the [F-18]FDG-PET/CT endpoint was shown to be decreased by 53-55% on treatment (Keijzers et al 2008; Milman et al 2012). Improvements in FVC over a 24 week period have been correlated with decreases in [F-18]FDG-PET/CT compared to baseline, with evidence of improvement by serial [F-18]FDG-PET/CT detected in sarcoid patients reported as early as 1-2 months (Brudin et al 1994; Braun et al 2008; Imperiale et al 2013). Furthermore, [F-18]FDG-PET/CT imaging was able to predict subsequent decreases in FVC and DLco (Sobic-Saranovic et al 2013; Vorselaars et al 2015).

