## 11.5 Analysis of secondary variable(s)

### 11.5.1 Efficacy / Pharmacodynamics

#### 11.5.1.1 [F-18]

The [F-18]FDG-PET/CT imaging data will be analyzed to identify the max standardized uptake values in the following categories:

- A maximum of 5 focal nodal uptake regions (mediastinal, hilar)
- A maximum of 5 focal regions of uptake in lung parenchyma
- A maximum of 5 extra-thoracic focal uptake regions on the whole body scan

[F-18]FDG-PET/CT mean

- A region of lung parenchyma, unaffected by focal lesion uptake

The mean of the SUVmax (resp. SUVmean) for each category will be taken to obtain one SUVmax value (resp. SUVmean) per patient / time point / category.

The mean percent change from baseline in SUVmax in the nodules after 12 weeks of treatment will be analyzed using ANCOVA with baseline SUVmax as a covariate and treatment and PET positivity (yes/no) as factors.

The same analysis as for the percent change from baseline in SUVmax in the nodules will be performed for the percent change from baseline in SUVmax in the lung parenchyma and the extra-thoracic regions, where available. It will also be repeated for SUVmean in the parenchyma.

The percentage of patients with at least 50% reduction of SUVmax in nodules will be analyzed via logistic regression with baseline SUVmax as a covariate and treatment and PET positivity (yes/no) as factors.

Also the change in the individual lung nodules will be examined, using a discretized scale of complete response (CR), partial response (PR), stable disease (SD) and progressive disease (PD) as in the oncology European Organization for Research and Treatment of Cancer criteria for [F-18]FDG-PET/CT. The proportion of individual responders and non-responders will be determined, based on PET. Patients who discontinue for lack of efficacy will be treated as a separate category in this summary.

The correlation between changes from initial FDG-PET scan in SUVmax and changes from baseline in FVC, FEV1, COAs, 6MWT distance will be assessed with graphical methods.

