### **11.7 Sample size calculation**

The sample size is determined by calculations with respect to the Bayesian analyses ([Fisch et al 2014](#)) (based on uninformative priors) of the change from baseline in the percent predicted FVC after 24 weeks of treatment. With 15 patients per group providing data at week 24 and assuming a standard deviation of 9% ([Judson et al 2014](#)), there is approximately 80% power to meet the efficacy criterion, if the true effect of ACZ885 over placebo is 7%.

Under the same assumption for the standard deviation, there is 10% probability of meeting the efficacy criterion if the true treatment difference is 0% (type I error rate).

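### The 50% SUVmax responder model makes no provision for an arm without responders, which at 15 to 19 patients per arm is a real possibility if the placebo rate is low

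*SAP*

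**What the plan says.** SAP 6.2.3, under the PET/CT heading: "The percentage of patients with at least 50% reduction of SUVmax in nodules will be analyzed via logistic regression". The terms are baseline SUVmax (continuous), treatment and PET positivity before randomisation. With the intercept that makes four parameters. Protocol 11.5.1.1 plans the same model: the responder percentage "will be analyzed via logistic regression with baseline SUVmax as a covariate", plus the same two factors.

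Neither document names a penalised or exact method, a type of confidence interval, or a fallback for a zero cell. Neither specifies a risk difference for this endpoint. The categorical summaries in SAP 6.2.2 use the CR/PR/SD/PD scale, which is a different classification.

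On size, protocol 3.1 plans about 38 randomised patients with 30 completers, and "Enrolled subjects will be randomized at a 1:1 ratio to receive treatment with either ACZ885 or placebo". Protocol 4 adds that after re-estimation at the interim analysis the "number of randomized patients may be increased up to a maximum of 90". Protocol 11.8 gives no power for secondary variables, and no responder rate is stated for either arm.

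**The concern.** Logistic regression fitted by maximum likelihood has no finite treatment coefficient when one arm has no responders. The software then returns a very large odds ratio with a huge standard error, or a convergence warning, and the Wald interval carries no information.

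The documents give some reason to expect few placebo responders. Background therapy must stay unchanged (protocol 3.5 and 5.2). Protocol 2.2 reports that low-dose prednisone hardly alters uptake on a second scan. The 50% threshold is close to what was seen under active drugs, where according to protocol 8.5.2.1 the "endpoint was shown to be decreased by 53-55% on treatment". None of this is a placebo rate, but it makes an empty placebo cell a possibility worth planning for.

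What is at stake is modest. Without a rule, the analyst either reports an uninterpretable odds ratio or picks a rescue method after seeing the unblinded data.

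**Working it through.** **The plan's own figure.** The only power statement concerns FVC: "With 15 patients per group providing data at week 24 and assuming a standard deviation of 9" percent, "there is approximately 80% power to meet the efficacy criterion, if the true effect of ACZ885 over placebo is 7" percent. With one-sided 10%: 7 / (9 × √(2/15)) = 2.130; 2.130 − 1.282 = 0.848; Φ(0.848) = 80.2%. It reproduces and confirms 15 per arm as the planning number. There is no stated figure for the responder analysis to reproduce.

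**Inputs.**
- n per arm: 15 (30 completers / 2) to 19 (38 randomised / 2). The number with measurable nodal SUVmax at week 12 is not stated. It could be lower if some patients have no nodal uptake.
- Placebo responder rate p: not given. Assumed range 2% to 20%.
- Active responder rate: assumed 50%. An empty active arm then has probability 0.5^15, about 0.003%, and can be ignored.

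**How plausible is that placebo range?** Assume a normal percent change with mean m and standard deviation s, so p = Φ((−50 − m)/s).
- m = 0: s = 25 gives Φ(−2.00) = 2.3%; s = 40 gives Φ(−1.25) = 10.6%.
- m = −10: s = 25 gives Φ(−1.60) = 5.5%; s = 40 gives Φ(−1.00) = 15.9%.

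These values of m and s are assumptions too, so the result is a guide and not evidence.

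**Chance of no placebo responder, (1 − p)^n.**

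| p | n = 15 | n = 19 | n = 45 |
|---|---|---|---|
| 2% | 74% | 68% | 40% |
| 5% | 46% | 38% | 10% |
| 10% | 21% | 14% | 1% |
| 15% | 9% | 5% | below 1% |
| 20% | 4% | 1% | below 1% |

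The last column takes all 90 patients as evaluable. If completion stayed at 30/38, 90 × 30/38 = 71, or about 36 per arm, and the first three entries would be 48%, 16% and 2%.

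**If the drug does nothing.** With the same rate p in both arms, the chance that at least one arm is empty is 1 − (1 − (1 − p)^n)². For p = 10% this is 37% (n = 15) or 25% (n = 19); for p = 5% it is 71% or 61%. The problem is therefore not tied to an effective drug.

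**What still works with an empty cell.** Take 0/15 placebo against 7/15 active, without covariates.
- Maximum likelihood: odds ratio infinite.
- Likelihood-ratio test: log-likelihood under separate rates is 7 ln(7/15) + 8 ln(8/15) = −10.364; under a common rate it is 7 ln(7/30) + 23 ln(23/30) = −16.298. Twice the difference is 11.9, p = 0.0006. The profile-likelihood 95% lower bound for the odds ratio is about 5.1, with no upper bound.
- Firth: in this 2×2 case it equals adding 0.5 to each cell, so (7.5 × 15.5)/(8.5 × 0.5) = 27.4. The standard error of the log is √(1/7.5 + 1/8.5 + 1/15.5 + 1/0.5) = 1.52, giving a Wald 95% interval of about 1.4 to 540. Profiling the penalised likelihood (bounds where twice the drop reaches 3.84) gives about 2.8 to 3,700.
- Risk difference: 7/15 − 0 = 47 percentage points. Wilson limits are 0.248 to 0.699 for 7/15, with an upper limit of 0.204 for 0/15. The Newcombe score interval is then 0.467 − √((0.467 − 0.248)² + 0.204²) = 17 points, to 70 points.

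**The case against.** The strongest reply is that the premise has no number behind it. A fall of 53-55% on other drugs says nothing direct about the spread of change on placebo, and the documents report no placebo figure. That stands: the risk is high only if the placebo rate is about 5% or lower, and small from 15% upward. A reader might infer that the model often fails. The documents do not support that without an assumed rate.

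A reader might also infer that the analysis cannot report the result most favourable to the drug. It can: the likelihood-ratio test and a one-sided profile bound remain available, as shown for 0/15 against 7/15. Only the point estimate and Wald inference break down, and neither document prescribes Wald.

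Higher failure rates can be obtained by simulating any separation in the four-parameter model, for example 27% instead of 21% at a 10% placebo rate, 50% active rate and 15 per arm. Those figures include separation through PET positivity or baseline SUVmax alone, where the treatment odds ratio may still be finite. They also rest on an assumed share of PET-positive patients (70%). The zero-cell figures are the relevant ones.

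Nor is there general support for saying that finite odds ratios are biased away from 1 at this size. Without covariates, at 10% against 50% with 15 per arm, the mean finite log odds ratio is 2.06 against a true ln(0.5/0.5) − ln(0.1/0.9) = 2.20.

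Finally, the stakes are low. The study is non-confirmatory, no decision rule uses this odds ratio, and the same SUVmax data are analysed as continuous percent change by ANCOVA. That limits the priority of the point but does not remove the gap.

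**Conclusion.** The gap is real and limited. The responder model has no rule for an empty arm. With 15 to 19 evaluable patients per arm, the chance of no finite maximum-likelihood treatment odds ratio runs from 74% / 68% at an assumed 2% placebo rate to 4% / 1% at 20%, and is 46% to 14% over the 5-10% range. An increase to 90 patients would largely remove it unless the placebo rate is about 5% or lower, but that increase is conditional and not the base plan.

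These figures assume independent patients with a common placebo rate and an active rate high enough that the active arm is not empty. The primary FVC criterion and the continuous SUVmax ANCOVA are unaffected. This is a worthwhile, nearly costless improvement to a supplementary secondary analysis, and not a threat to the trial's main conclusion.

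**What to change.** In SAP 6.2.3, specify that the responder model is fitted by Firth penalised-likelihood logistic regression with the same terms, and that intervals come from the profile penalised likelihood and not from Wald. Add that responder counts by arm and the unadjusted risk difference will be reported with a score or exact interval, whatever the counts.

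Do not offer exact logistic regression as an alternative. Conditioning on a continuous baseline SUVmax, with nearly all values distinct, typically leaves a degenerate or near-degenerate distribution.

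The cost is a sentence or two in the SAP and a standard software option, settled before unblinding. The downsides are slight shrinkage of the odds ratio toward 1 and intervals that remain wide: the method makes the estimate exist, but does not make it precise.

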### 7.2 Discontinuation of study treatment

#### Individual subject withdrawal

Subjects may voluntarily discontinue from the study for any reason at any time. They may be considered withdrawn if they state an intention to withdraw, fail to return for visits, or become lost to follow-up for any other reason.

Any patient who discontinues the study early will complete the Week 32 EOS visit. For those patients discontinuing after Week 12, the volumetric and HRCT exam should also be included as assessed on a case-by-case basis by the Sponsor.

If a subject discontinuation occurs for any reason, the Investigator must make every effort to determine the primary reason for a subject's discontinuation from the study and record this information on the CRF.

The investigator should discontinue study treatment for a given subject or discontinue the subject from study if, on balance, he/she believes that continuation would be detrimental to the subject's well-being.

If a liver or renal event occurs, follow guidelines outlined in [Appendix 1](#) and [Appendix 2](#) regarding discontinuation of study treatment.

Study treatment must be permanently discontinued under the following circumstances:

- Subject withdraws consent
- Pregnancy
- Severe allergic reaction or anaphylaxis following administration of the study drug
- Non-compliance as defined by missing more than one dose administration
- Emergence of the following adverse events:
  - Serious infections combined with neutropenia CTCAE v4.03 grades  $\geq 1$  (ANC  $< 1.5 \times 10^9/L$ )
  - Confirmed diagnosis of latent or active TB
  - Onset of any malignancy

- Any of the following laboratory abnormalities confirmed to be sustained by repeat assessment within 7 days after initial lab assessment:
  - Neutropenia CTCAE v4.03 grades  $\geq 2$
  - Thrombocytopenia CTCAE v4.03 grade 4
- Use of prohibited treatment as per [Table 5-1](#).
- Any other protocol deviation that results in a significant risk to the patient's safety

The appropriate personnel from the site and Novartis will assess whether study treatment should be discontinued for any subject whose treatment code has been broken inadvertently for any reason.

Subjects who discontinue study treatment should NOT automatically be considered withdrawn from the study. See [Section 8](#) for the required assessments of these subjects after discontinuation of study treatment.

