In this study, all patients will undergo whole-body head to mid-thigh [F-18]FDG-PET/CT imaging on a state-of-the-art, 3D PET/CT scanner with a reconstructed resolution of  $\leq$ 5 mm. Subjects with glucose levels above 11 mmol/L (200 mg/dL) should have their scan delayed or be rescheduled as appropriate. The blood glucose level measured prior to the radiotracer administration should be recorded in the image transmittal form (ITF). Subjects will have the radiotracer administered through an i.v. line, whereafter they will be positioned comfortably in a supine position to rest for 60 min, while the radiotracer distributes through the body. Near the end of this 60 min rest, subjects will be asked to void their bladder prior to the scanning procedure. A whole body low-dose attenuation CT will be acquired with a whole body effective dose of 1.5 mSv. Maximum injected radioactivity dose 200 MBq will result in a whole body effective dose of 4 mSv (ICRP 2008). Higher [F-18]FDG activities may be required in large or obese patients to ensure sufficient imaging quality, but it will not exceed 350 MBq. One further imaging scan will be performed at week 12 according to the schedule on enrolled patients with results quantitatively compared to baseline findings using centralized quantitative reading. Detailed information will be provided in the Parexel Imaging Investigator SOM. Total injected activity and body weight will be recorded and used to

compute standardized uptake values. The total dose for all PET/CT scanning (excluding HRCT) in this protocol will be maximally 11 mSv, or 16 mSv in larger or obese patients requiring a higher [F-18]FDG injected dose.

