**Table 4-1 Protocol deviation codes and analysis sets**

Category Deviation code	Text description of deviation	Data exclusion
Subjects are excluded from all (safety) analysis in case of these PDs:		Exclude subject completely from all (safety) analysis sets
INCL01	Deviation from inclusion criteria: Written informed consent was not obtained before any study assessment was performed	Yes
Subjects are excluded from PK analysis in case of these PDs:		Exclude subject from PK analysis set
INCL01	Deviation from inclusion criteria: Written informed consent was not obtained before any study assessment was performed	Yes

Category Deviation code	Text description of deviation	Data exclusion
Subjects are excluded from PD analysis in case of these PDs:		
INCL01	Deviation from inclusion criteria: Written informed consent was not obtained before any study assessment was performed	Exclude subject from PD analysis set Yes
Subjects are excluded from PD analysis after the PD date in case of these PDs:		
COMD01	Prohibited medication used	Exclude subject from PD analysis set after the date of the event Yes
Subjects are excluded from PK and PD analysis in case of these PDs:		
INCL01	Deviation from inclusion criteria: Written informed consent was not obtained before any study assessment was performed	Exclude subject from PK and PD analysis sets Yes

If updates to this table are needed, an amendment to the SAP needs to be implemented prior to DBL.

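### The 50% SUVmax responder analysis gives no score to patients who take prohibited medication, or leave for lack of efficacy without a scan, before the single Week 12 PET

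*SAP*

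**What the plan says.** **Model.** SAP 6.2.3, under [F-18]FDG-PET/CT: "The percentage of patients with at least 50% reduction of SUVmax in nodules will be analyzed via logistic regression with baseline SUVmax as a covariate", with treatment and PET positivity as factors. Protocol 11.5.1.1 plans the same model. Neither says how to score a patient without a usable follow-up scan.

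**Scans.** Protocol 8.5.2.1 plans one follow-up PET: "One further imaging scan will be performed at week 12 according to the schedule on enrolled patients". For early discontinuers, Protocol 7.2 requires the EOS visit and adds only CT imaging, and only later in the study: "For those patients discontinuing after Week 12, the volumetric and HRCT exam should also be included". No early-termination PET is named there.

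**Stopping drug.** Protocol 7.2 also says: "Subjects who discontinue study treatment should NOT automatically be considered withdrawn from the study".

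**Prohibited medication.** For deviation COMD01, SAP Table 4-1 instructs: "Exclude subject from PD analysis set after the date of the event". SAP 6.1.5 worries about bias from this exclusion, "as concomitant medication increase is primarily due to poor response".

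**Lack of efficacy.** In the CR/PR/SD/PD summary of SAP 6.2.2, "patients who discontinue for lack of efficacy will be treated as a separate category in this summary". Nothing equivalent appears for the 50% responder model.

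**Sensitivity analyses.** For PET, SAP 6.2.3 says: "The same sensitivity and subgroup analyses as the primary may also be performed, if deemed necessary". The only named missing-data analysis for the primary is an LOCF run in SAP 6.1.5, which is itself optional.

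**The concern.** A responder rate is meaningful only if patients for whom treatment has failed count against it. Here the exclusion rule depends on outcome, by the SAP's own account: patients move to prohibited medication mainly because they respond poorly, and Table 4-1 then discards their later PD data. With a single follow-up scan, a COMD01 event before Week 12 leaves no outcome at all. The patient leaves both numerator and denominator.

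Patients who leave for lack of efficacy before Week 12 and are not scanned are in a similar position, though by omission and not by rule. No score is defined, and logistic regression software discards records with a missing outcome.

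At stake is the reading of the PET data, which Protocol 2.2 and 8.5.2.1 present as early evidence of an anti-inflammatory effect. Removing failures raises the observed response rate in the arm that loses them. With about 19 patients per arm, a few such patients move the comparison visibly. If the rule is not set in advance, it will be chosen once the data are in hand.

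**Working it through.** **The plan's own figures.** Protocol 11.8 gives no power for secondary variables, so there is no responder figure to reproduce. The primary power in Protocol 11.7 does reproduce: SE = 9 × √(2/15) = 3.29; 7/3.29 = 2.13; 2.13 − 1.28 = 0.85; power = Φ(0.85) = 80%. It says nothing about the responder endpoint.

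**Inputs from the documents.** About 38 randomized and 30 completers targeted (Protocol 3.1), with 1:1 allocation, so 19 per arm.

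**Assumptions, not in the documents.** Constant loss over 24 weeks; every lost patient is a failure; responders 8 of 19 on ACZ885 and 2 of 19 on placebo.

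**Step 1: losses by Week 12.** Planned loss is 8/38 = 21%. At a constant rate, the share lost by the halfway point is 1 − √(30/38) = 0.111, and 0.111 × 38 = 4.2, or about four patients. COMD01 exclusions among patients who stay in the study would be additional.

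**Step 2: effect of dropping four failures.** With a lost on ACZ885 and b on placebo, the complete-case rates are 8/(19 − a) and 2/(19 − b). Scored as non-responders, they stay at 8/19 = 42.1% and 2/19 = 10.5%, a difference of 31.6 points.

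| Lost, ACZ885 / placebo | ACZ885 | Placebo | Difference | Shift from 31.6 |
|---|---|---|---|---|
| 0 / 4 | 8/19 = 42.1% | 2/15 = 13.3% | 28.8 | −2.8 |
| 1 / 3 | 8/18 = 44.4% | 2/16 = 12.5% | 31.9 | +0.3 |
| 2 / 2 | 8/17 = 47.1% | 2/17 = 11.8% | 35.3 | +3.7 |
| 3 / 1 | 8/16 = 50.0% | 2/18 = 11.1% | 38.9 | +7.3 |
| 4 / 0 | 8/15 = 53.3% | 2/19 = 10.5% | 42.8 | +11.2 |

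**Step 3: can it create an effect from none?** Take 6 true responders per arm (31.6% each, OR 1.00) and, as an upper bound, let all 8 planned non-completers be failures lost before Week 12.

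- Lost 4/4: 6/15 = 40.0% in both arms, OR 1.00. Both rates are inflated; the null comparison is not.
- Lost 6/2: 6/13 = 46.2% against 6/17 = 35.3%, OR = (6/7)/(6/11) = 1.57.
- Lost 2/6: the mirror image, OR 0.64.
- Lost 8/0: 6/11 = 54.5% against 31.6%, OR = (6/5)/(6/13) = 2.60.

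The odds ratios here are unadjusted. Unequal loss of failures shifts the comparison toward the arm that loses more of them.

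**The case against.** Several points on the other side stand.

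- **Complete-case analysis is not stated.** A reader might infer that the SAP tells the analyst to drop every treatment failure. It does so only for data after a COMD01 event. For other losses, deletion is the software default, and the opening of SAP section 6 says all PD-set subjects are included. That sentence supplies no outcome value, however.
- **Stopping drug is not withdrawal.** Under Protocol 7.2 a patient may stop study drug, stay in the study and be scanned at Week 12. Such a patient has an outcome unless a COMD01 event removes it. Before Week 12, leaving for lack of efficacy is a subset of early stopping, not a further source of loss.
- **The LOCF analysis addresses this bias.** If the initial scan may be carried forward, the change is 0%, which is non-response. But the SAP does not say that it may, the run is conditional for FVC, and for PET it is only a possibility.
- **The two response displays differ.** The CR/PR/SD/PD summary grades individual lung nodules; the responder model uses the per-patient mean nodal SUVmax. The separate category in the summary shows that such failures were thought to need handling. It does not make the two outputs contradictory.
- **The size is small against the noise.** With 8/19 and 2/19, the SE of the difference is √(0.421 × 0.579/19 + 0.105 × 0.895/19) = 0.13, about 13 points, so every shift in the four-loss table is below one SE. This limits the practical effect, but does not justify an outcome-dependent denominator.
- **Early failures may be few.** Protocol 2.2 expects lung function to change later than PET, and the exacerbation definition in Protocol 6.10 requires a decline lasting at least one month.

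**Conclusion.** The concern holds. COMD01 failures before Week 12 leave the 50% responder analysis by a stated rule, and lack-of-efficacy withdrawals without a scan would leave it by default. The only mitigation is optional and not specified for PET.

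A reader might infer that the ACZ885 benefit is therefore overstated. The documents do not support that: the response rate rises in whichever arm loses more failures, so the benefit is understated if that arm is placebo. The size is unknown, because the documents give neither the losses before Week 12 nor any expected response rate. The −3 to +11 points for four losses rest on the assumed 8/19 and 2/19, constant attrition, and all lost patients being failures. The eight-loss odds ratios are upper-bound illustrations. The imaging rows of the assessment schedule cannot be read in the public copy, so the absence of an early-termination PET rests on Protocol 7.2 and 8.5.2.1 and the schedule footnote on early discontinuation.

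This is a secondary analysis in a non-confirmatory study. The primary conclusion is unaffected, but the rule should be settled before database lock.

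**What to change.** Add one paragraph to SAP 6.2.3.

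1. **Denominator:** PD-set patients with measurable nodal uptake at the initial scan.
2. **Failures:** score as non-responders those who, before the Week 12 PET, discontinue for lack of efficacy or have a COMD01 event involving an immunosuppressant or steroid. State that this scoring applies despite the data exclusion in Table 4-1.
3. **Post-event scans:** do not use them as observed. Protocol 3.2 itself says high-dose steroids attenuate the PET signal, so a failing patient could appear to respond.
4. **Other missing Week 12 scans:** report both complete case and non-responder scoring. Non-responder scoring of unrelated losses is not reliably conservative. In the example above, if four unrelated losses were all on placebo, it would raise the difference from 28.8 to 31.6 points; if all were on ACZ885, it would lower it from 42.8 to 31.6.

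The cost is that paragraph and one extra run, with no new data collection. The choice in item 4 remains a convention, which is why both results should be shown.
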